2. LAY SUMMARY

The aim of this RCT is to evaluate the impact of digital detox on mental health in 18-29 yo students from Austria. Screen time (less than 2 hours per day) as well as social media use (less than 1 hour per day) should be reduced for a period of 3 weeks and the effects should be compared to a controlled group.

A sample of N > 96 should be recruited through newsletter, notices and advertising on social media. The inclusion criteria are more than 3 hours of screen time per day, primarily on social media, and no psychiatric illness for which they are being treated.

After informing and signed the consent form, the participants have to download an App (ESMira®), which processes the whole study. The first step is to fill out sociodemographic data, smartphone usage and mental health questionnaires. After controlling for inclusion and exclusion criteria, ESMira will randomize into intervention (A) and controlled group (B).

The participants in the intervention group (A) should continue their social media use and smartphone screen time unchanged for the first 10 days (Baseline= t1.) After that, the participants should limit their use of social media, such as Instagram, TikTok, Snapchat, Facebook, or similar sites to one hour per day and the complete screen time under two hours per day. To comply with that, participants should use the limiter function of there smartphone or download an additional app. Screen time of the smartphone and the social media use will be tracked automatically or via uploading a screenshot. At the end of the intervention (t2), the mental health questionnaires will be collected again. Afterwards there are no further tasks for the participants in the intervention group (A), social media use is possible again without restrictions, screen time and social media use will be tracked until 3 month follow up (t3). During the study period participants will be asked to additionally wear a fitness tracker to measure daily movement as well as sleep behavior.

The controls group (B) will be asked to continue their social media use and screen time unchanged for 3 month, after that the will be asked to fill out the mental health questionnaires again.

Hypotheses

The primary hypothesis of the study is that mental health, particularly stress, depressive symptoms, and sleep quality will improve after the intervention (t2) compared to the control group as well as compared to baseline.

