3. SYNOPSIS

Trial Title	Smartphone Screentime Reduction improves mental health: A randomized clinical trial				
Internal ref. no. (or short title)	EK GZ 67/2021-2024				
Trial registration	https://osf.io/a9k76				
Sponsor	N.a.				
Funder	N.a.				
Clinical Phase					
Trial Design	Two group, not blinded, randomized controlled trial with a follow up.				

Trial Participants	Healthy adults could participate if thes were 1) between 18 - 29 yo, 2) owning a smartphone and using it at least 3 h/d, and 3) no diagnosed or treated mental disorder, no ongoing psychotherapy or psychopharmaceutic therapy (self-report). Moderately elevated levels in mental health screening questionnaires were no exclusion criteria.			
Sample Size	With a small to medium effect size (Cohens d= 0.45; power .8, significance level < .05, icc = .05), significant results can be expected with a completed data set of minimum 40 people per group. Considering a drop-out rate of 20%, at least 50 people per group were recruited.			
Planned Trial Period	The total study period will be 12 weeks: Screening for eligibility, 10 days baseline phase, 3 weeks intervention, 6 weeks post intervention to follow-up			
Planned Recruitment period	Study protocol submission: August 20, 2023; Approval by Ethical committee October 23, 2023; Information on Social Media and notices at University; Registration November 8, 2023; Screening for Eligibility November 8-10, 2023 Objectives Outcome Measures Timepoint(s)			
Primary	 Depressive Symptoms Well-being Stress Sleep Quality 	 Patient Health Questionnaire (PHQ-9) World Health Organization wellbeing questionnaire (WHO-5) Perceived Stress Questionnaire (PSQ-20) Insomnia Severity Index (ISI) 		
Secondary	 Problematic Smartphone Use Disordered Eating Body Appreciation Anxiety 	 Smartphone Addiction Scale (SAS-SV) SCOFF BAS-2 GAD-7 		
Intervention(s) •	The intervention is reducing smartphone screen time <2/h for 3 weeks. Smartphone screen time will be assessed weekly in both groups using the smartphones' built-in screen time measurements. Weekly, participants will be asked to upload a screenshot from their screen time from the previous week.			

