11. STATISTIC ANALYSIS PLAN

We will use the statistic software IBM SPSS Statistics (IBM Corp., Armonk, NY, USA) to analyze the data. χ^2 -Test and independent samples tests will be used to examine differences at baseline (t0) regarding age, gender, smartphone screen time, physical activity per week, and mental health indicators between the control and the intervention group.

Clinical Trial Protocol Template version 14.0

CONFIDENTIAL

To examine the effect of reduced smartphone screen time on the mental health indicators, repeated measurements ANOVAs (rm-ANOVA) will be applied. The primary hypotheses focuses on the difference between t0 (baseline) and t1 (post-intervention) between control group and intervention group (between group effect). In a secondary analysis, the follow-up time point (t2) will also be included.

Group allocation (control vs. intervention) will be the between-group factor, time will be the within-group factor (t0, t1, t2). Furthermore, a sub-group analysis (rm-ANOVA) will be applied of those, who strictly adhered to the 2h smartphone screen time limit during all three weeks. In case of baseline group-differences in the mental health indicators, these variables will be added as a covariate in the rm-ANOVA. If the sphericity assumption will be violated, the Greenhouse-Geisser correction will be applied. In the post hoc tests, Bonferroni correction will be applied to adjust for multiple comparisons.

Missing values will be estimated with via maximum likelihood estimation.

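### The primary hypothesis in Section 2 adds a comparison with baseline that is not part of the between-group primary contrast in Section 11, and the plan never gives that comparison a role

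*Combined protocol and SAP*

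**What the plan says.** Section 2 (Lay Summary), under its Hypotheses heading, gives the primary hypothesis two comparators. Mental health "will improve after the intervention (t2) compared to the control group as well as compared to baseline".

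Section 11 (Statistic Analysis Plan) gives it one: "The primary hypotheses focuses on the difference between t0 (baseline) and t1 (post-intervention) between control group and intervention group". The model is a repeated-measures ANOVA with group as the between factor and time as the within factor. Post hoc tests are Bonferroni-corrected. Section 11 gives a within-group change no role as a success criterion, and no section says which statement takes precedence.

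The Synopsis fixes the calendar with "Screening for Eligibility November 8-10, 2023" and a schedule of "10 days baseline phase, 3 weeks intervention, 6 weeks post intervention to follow-up". Its sample size statement is that "significant results can be expected with a completed data set of minimum 40 people per group", for d = 0.45, power .8, significance level .05 and icc .05.

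The trial is not blinded (Sections 6 and 8.5). Section 5 measures both groups at baseline, post-intervention and follow-up.

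**The concern.** A change within the intervention group is an uncontrolled before-after comparison. Everyone enters within the same three days, so calendar time is practically identical for all participants. Season, the term calendar and repeat testing would move both groups together. The concurrent control group separates such common drift from the intervention; a comparison with baseline does not.

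What is at stake depends on how the two halves of the Section 2 sentence combine, and the plan does not say:

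- If either comparison could support the claim, favourable drift alone could be reported as a benefit.
- If both are required, a real benefit over control could be missed because both groups worsened.

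Time is a within factor and post hoc tests are planned. A significant within-group change could therefore be produced under Section 11 and cited as confirming the Section 2 hypothesis.

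**Working it through.** **The plan's own figure.** The 40 completers per group is approximately recovered by a repeated-measures ANOVA calculation with f = d/2 = 0.225, m = 2 measurements, and icc .05 used as the correlation between measurements.

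- Between-factor effect: λ = N f² m / (1 + (m − 1)ρ). With N = 84, λ = 84 × 0.050625 × 2 / 1.05 = 8.10, power .803, so 42 per group.
- Group-by-time interaction: λ = N f² m / (1 − ρ). With N = 76, λ = 76 × 0.050625 × 2 / 0.95 = 8.10, power .802, so 38 per group.

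These bracket 40, so n = 40 is used below.

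**Calendar.** 10 days + 21 days = 31 days. Screening on 8-10 November puts post-intervention at about 9-11 December 2023. This takes the baseline questionnaires at entry, which Sections 2 and 9 call the first step.

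**Assumptions not in the documents.** These are the size and direction of drift (0.2 and 0.3 SD shown) and the baseline-to-post correlation ρ (.5 and .7, shown beside the documents' own .05). The test is taken as two-sided at .05, unadjusted; the plan does not state sidedness.

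**Before-after test in the intervention group.** The SD of change is √(2(1 − ρ)). The noncentrality is change × √40 / √(2(1 − ρ)), and the critical t on 39 df is 2.023. With no intervention effect and favourable drift, the probability of a significant improvement is:

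| ρ | SD of change | drift 0.2 SD: noncentrality, probability | drift 0.3 SD: noncentrality, probability |
|---|---|---|---|
| .05 | 1.378 | 0.918, 14% | 1.376, 27% |
| .5 | 1.000 | 1.265, 23% | 1.897, 46% |
| .7 | 0.775 | 1.633, 36% | 2.449, 67% |

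Without drift the figure is 2.5%.

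**Adverse drift with a real effect.** With a benefit of 0.45 SD over control and both groups worsening by 0.2 SD, the net within-group change is 0.45 − 0.20 = 0.25 SD. The before-after test is then significant in 34% of trials at ρ = .5 and 51% at ρ = .7. Without drift the figures are 79% and 95%.

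**Between-group contrast.** The expected difference in change is (effect + drift) − drift = effect, so common drift cancels. The false-benefit rate stays at 2.5%. In 20,000 simulated trials at ρ = .5 it was 2.6% under drift of 0.2 and of 0.3 SD.

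**Combining the two comparisons** (simulation, ρ = .5, no effect, drift 0.2 / 0.3 SD):

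- Either suffices: false-positive rate 24% / 46%.
- Both required: 2.3% / 2.6%.

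When both are required and the true effect is 0.45 SD, 0.2 SD of common worsening lowers joint power from about 49% to 28-29% at ρ = .5, and from about 72% to 47-48% at ρ = .7. The between-group test alone stays at 51% and 73%.

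**The case against.** The strongest reply is that the operative text is already right. Section 11 makes the between-group difference primary, and the two-comparator wording appears only in a lay summary with no test, threshold or decision rule. It could even be loose wording for change from baseline compared with control. Much of this stands: the planned primary analysis is sound. But Section 2 labels the sentence the primary hypothesis, no precedence is stated, and Section 11 leaves room for within-group tests.

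A reader might infer that the plan carries a false-positive rate of 23% to 67%. The documents do not support that. The wording reads most naturally as requiring both comparisons, and type I error is then not inflated. The documents also report no drift in either direction, so a worsening towards winter is equally an assumption. At the only correlation-like value they give, .05, the figures are 14% and 27%. Bonferroni correction would lower them too: over an assumed three comparisons (the family is not stated), 0.2 SD of drift gives 12-21% at ρ = .5 to .7. It would also lower before-after power, and it does not remove the drift.

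A reader might also infer that the control group removes expectation effects. It does not. In an unblinded trial where one group undertakes the reduction and the other continues as before, expectation may differ by group. The between-group contrast cancels only what is common to both.

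**Conclusion.** The point holds as a conflict of definition. Section 2 names two comparators, Section 11 names one, and the role of the baseline comparison is undefined. Its consequence is conditional:

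- If the baseline comparison alone could support the claim, assumed favourable drift of 0.2-0.3 SD gives a spurious improvement in 14-67% of trials over correlations of .05 to .7.
- If both comparisons are required, the only cost is power. With 0.2 SD of adverse drift, the before-after test succeeds in 34-51% of trials instead of 79-95%, at correlations of .5 to .7.

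These figures illustrate how the claim depends on drift; they do not predict what this trial will show. Either way, the baseline comparison cannot say whether the intervention works, and the between-group contrast already in the plan can. The change is worth making because it settles, at almost no cost, what the trial may conclude.

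**What to change.** 1. In Section 2, delete the clause that adds the comparison with baseline. Restate the primary hypothesis as the Section 11 contrast: the difference between groups in change from baseline to post-intervention.
2. Reconcile the timepoint labels. Post-intervention is t2 in Sections 2 and 9 but t1 in Section 11, where t2 is follow-up, as it is in Section 5. Without this step the reworded hypothesis would still point to a different visit from the analysis.
3. Reconcile the control-group schedule. Section 2 mentions repeat questionnaires for controls only after 3 months, and Section 9 only after follow-up, whereas Section 5 measures both groups post-intervention. The primary contrast needs that control measurement.
4. In Section 11, add that within-group changes are reported descriptively, as means with confidence intervals, and are not used to claim an effect.

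The cost is a few sentences. If the Section 5 schedule is the one followed, no visits, data or participants are added. The sponsor gives up a before-after claim that the design cannot support.

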3. SYNOPSIS

Trial Title	Smartphone Screentime Reduction improves mental health: A randomized clinical trial				
Internal ref. no. (or short title)	EK GZ 67/2021-2024				
Trial registration	https://osf.io/a9k76				
Sponsor	N.a.				
Funder	N.a.				
Clinical Phase					
Trial Design	Two group, not blinded, randomized controlled trial with a follow up.				

Trial Participants	Healthy adults could participate if thes were 1) between 18 - 29 yo, 2) owning a smartphone and using it at least 3 h/d, and 3) no diagnosed or treated mental disorder, no ongoing psychotherapy or psychopharmaceutic therapy (self-report). Moderately elevated levels in mental health screening questionnaires were no exclusion criteria.			
Sample Size	With a small to medium effect size (Cohens d= 0.45; power .8, significance level < .05, icc = .05), significant results can be expected with a completed data set of minimum 40 people per group. Considering a drop-out rate of 20%, at least 50 people per group were recruited.			
Planned Trial Period	The total study period will be 12 weeks: Screening for eligibility, 10 days baseline phase, 3 weeks intervention, 6 weeks post intervention to follow-up			
Planned Recruitment period	Study protocol submission: August 20, 2023; Approval by Ethical committee October 23, 2023; Information on Social Media and notices at University; Registration November 8, 2023; Screening for Eligibility November 8-10, 2023 Objectives Outcome Measures Timepoint(s)			
Primary	 Depressive Symptoms Well-being Stress Sleep Quality 	 Patient Health Questionnaire (PHQ-9) World Health Organization wellbeing questionnaire (WHO-5) Perceived Stress Questionnaire (PSQ-20) Insomnia Severity Index (ISI) 		
Secondary	 Problematic Smartphone Use Disordered Eating Body Appreciation Anxiety 	 Smartphone Addiction Scale (SAS-SV) SCOFF BAS-2 GAD-7 		
Intervention(s) •	The intervention is reducing smartphone screen time <2/h for 3 weeks. Smartphone screen time will be assessed weekly in both groups using the smartphones' built-in screen time measurements. Weekly, participants will be asked to upload a screenshot from their screen time from the previous week.			

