11.1. Sample Size Determination

According to the power analysis 40 per group should finish the study per group, in case of 20% drop outs, a minimum of 96 participants should be included.

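### A minimum of 96 enrolled leaves 38.4 completers per group, not 40, and the claimed 80% power for d = 0.45 is not supported for the primary t0–t1 contrast because d and the icc are undefined

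*Combined protocol and SAP*

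**What the plan says.** The Synopsis (Section 3) gives the assumptions as "Cohens d= 0.45; power .8, significance level < .05, icc = .05" and concludes that "significant results can be expected with a completed data set of minimum 40 people per group". It then inflates for attrition: "Considering a drop-out rate of 20%, at least 50 people per group were recruited", which is 100 in total.

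Section 11.1 repeats the 40 finishers per group and the 20% loss but arrives at a different total: "in case of 20% drop outs, a minimum of 96 participants should be included". Sections 2 and 9 both carry a matching bound: "A sample of N > 96 should be recruited through newsletter".

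Section 11 specifies repeated-measures ANOVA and describes the primary comparison this way: "The primary hypotheses focuses on the difference between t0 (baseline) and t1 (post-intervention) between control group and intervention group (between group effect"). Baseline values enter the model only conditionally: "In case of baseline group-differences in the mental health indicators, these variables will be added as a covariate in the rm-ANOVA".

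No section states which test was powered, which SD standardises d, what the icc refers to, or whether the 5% level is one- or two-sided.

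**The concern.** The same two inputs, 40 completers per group and 20% loss, lead to 100 in one section and 96 in another. Both cannot be right, and three sections carry the lower figure.

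The power statement is the larger matter. A standardised difference of 0.45 with 40 per group is well short of 80% power in an ordinary two-group comparison, so the claim must draw on the repeated measurements. Whether it can do so for a t0–t1 contrast depends on what d means and on the pre-post correlation. The first is undefined, and the second is absent unless the icc of .05 is meant to be it. Readers will judge a null result against the stated 80%. If the true figure is nearer 50%, such a result says little about whether an effect of 0.45 exists.

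**Working it through.** **Enrolment.** Inputs: 40 completers per group and 20% drop-out (Sections 3 and 11.1).

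- Required: 80 / (1 − 0.20) = 100, or 50 per group. This is the Synopsis figure.
- 80 × 1.2 = 96 reproduces the Section 11.1 figure. It adds 20% of the completers instead of allowing for a loss of 20% of those enrolled.
- 96 × 0.8 = 76.8 completers, or 38.4 per group, 1.6 short of 40.
- 96 enrolled yields 80 completers only if drop-out is at most 1 − 80/96 = 16.7%.
- Reading the bound in Sections 2 and 9 strictly does not cure this: 97 × 0.8 / 2 = 38.8.

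**Reproducing 40 per group.** Inputs: d = 0.45, power .8, 5% level, icc = .05 (Section 3). Equal allocation and two-sided tests are assumed; the ANOVA F test is non-directional.

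A plain two-sample t test has 51% power at 40 per group and needs 79 per group for 80%. Of the calculations tried, only one type comes close to 40: a two-measurement repeated-measures ANOVA with f = d/2 = 0.225, m = 2 and the icc read as a correlation ρ = .05 between measurements. With N = 80:

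- Between-group factor: λ = f²Nm / (1 + (m − 1)ρ) = 0.225² × 80 × 2 / 1.05 = 7.71; power 78% (84 in total needed for 80%).
- Group-by-time interaction: λ = f²Nm / (1 − ρ) = 0.225² × 80 × 2 / 0.95 = 8.53; power 82% (76 in total needed).

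With three measurements the totals needed are 60 and 62, so that version does not give 80.

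**What those two versions require.**

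- The between-group factor tests the difference averaged over t0 and t1. An average of 0.45 SD needs a difference at t0 as well, and randomisation implies none. If 0.45 SD exists only at t1, the average is 0.225 SD, f = 0.1125, and power is 28%.
- For the interaction, f equals the difference in change divided by 4, in raw SD units. So f = 0.225 means a net change of 4 × 0.225 = 0.90 SD, twice the stated d.

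**Power for the Section 11 contrast.** The t0–t1 group-by-time test is equivalent to a two-sample t test on change scores. A raw-SD difference of 0.45 that appears by t1 becomes 0.45 / √(2(1 − ρ)) in change-score SD units. At 40 per group, 80% power needs 0.634 in change-score SD units, which is 0.634 × √(2(1 − ρ)) in raw SD.

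| Reading of d | Pre-post correlation ρ | Power for d = 0.45 | Difference detectable at 80% |
|---|---|---|---|
| Change-score SD | not needed | 51% | 0.63 change-score SD |
| Post-intervention only | not needed | 51% | 0.63 SD |
| Raw SD, change contrast | .05 (icc read as ρ) | 30% | 0.87 SD |
| Raw SD, change contrast | .5 (assumed) | 51% | 0.63 SD |
| Raw SD, change contrast | .6 (assumed) | 60% | 0.57 SD |
| Raw SD, change contrast | .7 (assumed) | 73% | 0.49 SD |
| Raw SD, change contrast | .75 (assumed) | 80% | 0.45 SD |

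Exactly 80% is reached at ρ = .748. A simulation with 40,000 runs per setting gave 30%, 51%, 73% and 80% at ρ = .05, .5, .7 and .75.

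**Cost of the 96.** Going from 40 to 38.4 per group moves the between-factor figure from 78.3% to 76.6% and the post-only figure from 51.1% to 49.5%.

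**The case against.** The enrolment conflict is small. The Synopsis already has the right inflation, the bound in Sections 2 and 9 is compatible with 100, and under the interaction calculation even 76.8 completers give 80.6%. That fairly describes its size. The conflict remains, because the completer target is the plan's own and 96 does not meet it.

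On power, the best defence is that about 40 per group can be reproduced, and that Section 11 itself speaks of a between-group effect. The authors may have used standard software correctly, so the statement is under-specified and not shown to be miscalculated. That stands, and it is why the conclusion is that the claim is unsupported. It does not rescue the primary contrast: one version needs a difference at baseline and the other needs twice the stated effect.

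Every lower figure also depends on a choice the documents do not make. A correlation of .05 would be an odd planning value for the same questionnaire repeated weeks apart, so 30% is not the likeliest scenario. A one-sided test would give 64% at ρ = .5 and 82% at ρ = .7, but nothing in the plan says one-sided and the F test is not. Baseline adjustment by ANCOVA would give 63% at ρ = .5 and just under 80% (79.5%) at ρ = .7, but the plan adjusts only if the groups differ at baseline. These points widen the range of possible power; none of them establishes 80%.

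**Conclusion.** The concern holds in both parts and should be fixed.

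- The minimum of 96 is wrong on the plan's own inputs and contradicts the Synopsis. It is a consistency error with a minor effect on power.
- The 80% power for d = 0.45 is not supported for the primary contrast. On readings that fit a randomised t0–t1 comparison, power at 40 per group is 51% with d in change-score SD units. With d in raw SD it depends on the pre-post correlation, and is below 80% unless that correlation is about .75 or more.

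The arithmetic on 96 needs no assumption. The power figures assume equal allocation, a two-sided 5% test and complete data on 40 per group. The correlations from .5 to .75 are illustrative, because the documents give none.

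**What to change.** 1. In Section 11.1 replace the 96, and in Sections 2 and 9 replace the bound based on it, with at least 100 (50 per group; 80 / 0.8).
2. In Sections 3 and 11.1, state the power for the planned t0–t1 group-by-time test. Say whether d is a post-intervention difference or a change, and in which SD. Give the assumed pre-post correlation with its basis, state that the test is two-sided, and delete the icc or replace it with a defined quantity.

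An example, to be completed with the authors' own correlation:

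> With 40 completers per group and a two-sided 5% level, the t0–t1 group-by-time test has 80% power for a between-group difference of 0.63 SD of the change score. For a post-intervention difference of 0.45 raw SD, power is 80% only if the pre-post correlation is about .75; it is 73% at .7 and 51% at .5.

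ANCOVA power should be quoted only if Section 11 is changed to make ANCOVA the primary analysis.

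The cost is wording. No participants are needed beyond the Synopsis figure, although the minimum in Section 11.1 rises from 96 to 100. The authors must commit to a definition of d and a correlation, and the stated power becomes less favourable. The rewording discloses the limited power; it does not increase it.
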